5.4 Subjects lost to follow-up

If a subject fails to return for the follow-up visit, a letter will be sent to their most current mailing address, reminding them of their study obligations. Additionally, the subject will be contacted at their last known home telephone number. When all reasonable attempts to locate the subject have been exhausted, including contacting the subject's general practitioner, the subject will be considered lost to follow-up. Documentation is required for all attempts to locate the subject.

6 Study Design

The study aims to include 176 evaluable patients; however, enrolment of up to 228 patients will be allowed in the event the data is needed to compensate for "roll in" patients, missing or censored outcome data, patient withdrawal, or too small a mITT population to test the primary endpoint for the hypothesis as designed.

There are three FDA cleared stent retrievers indicated for neuro-thrombectomy: Merci, Trevo and Solitaire. The Trevo and Solitaire devices conducted randomized trials using the Merci device as a control in support of premarket clearance. The results, of these trials provide a valid scientific basis for the establishment of a composite performance goal derived using a Bayesian meta-analysis. At 176 evaluable patients and 64% successful endpoint achievement the ARISE II study is expected to allow the EmboTrap device, with 90% power, to claim non-inferiority based on a one-sided test at the 0.025 significance level to U.S. approved predicate devices.

The success rate in ARISE II for the population of interest will be assessed using an Intention To Treat basis and also a modified Intention To Treat analysis.

Vessel recanalization and revascularization based on the final post-EmboTrap device use angiogram is a clearly measurable efficacy endpoint and less susceptible to influencing factors based on the patient population and care than other patient related outcomes.

6.1 Site Selection

The sponsor or a representative of the sponsor will assess each potential site to ensure the principal investigator and their staff has the facilities and expertise required for the study. Sites will be selected based upon a site assessment considering appropriate facilities, and the qualifications of the investigator(s). Individual investigators will be evaluated by the Sponsor based on experience with the intended procedure(s), and ability to conduct the study according to the study protocol.

Principal investigators and sites will be selected based upon the following factors:

- Previous experience with clinical research and mechanical thrombectomy procedures.
- Experience in conducting controlled, clinical studies.
- Willingness to observe confidentiality at all times.
- Currently treating subjects who meet the inclusion/exclusion criteria.
- Ability to enroll an adequate number of subjects.
- Ability to perform required clinical testing, including: angiography, CT, and/or MRI.
- Ability and willingness to provide the sponsor's representatives, FDA and local regulatory authorities access to the hospital records, study files, and subject files as they pertain to the study.
- Willingness to participate, including compliance with all aspects of the study.

- Adequate staffing to conduct the study. This includes:
 - Principal Investigator (PI): Responsible for overall clinical management of subjects enrolled at his/her institution. Assumes overall responsibility and accountability for the clinical team and for data obtained from each subject participating in the study. Ensures compliance with the protocol, applicable laws, and applicable regulations; ensures informed consents are signed, and reviews and signs eCRFs indicating documents are accurate and complete.
 - Sub/Co-Investigator(s) (Sub-I/Co-I): Responsible for study activities in coordination with PI and in accordance to the investigational plan. Assume the responsibility of the PI should the PI resign from the study. A site is not required to have a co-investigator.
 - Study Coordinator: Assists PI with study activities as delegated by the PI, including tracking subjects involved in the study, scheduling testing and follow-up visits, maintaining study records, completing eCRFs to the sponsor in a timely manner.

6.2 Inclusion criteria

Study subjects must meet all of the inclusion criteria listed below:

1. The patient or the patient's legally authorized representative has signed and dated an Informed Consent Form.
2. Aged between 18 years and 85 years (inclusive).
3. A new focal disabling neurologic deficit consistent with acute cerebral ischemia.
4. NIHSS score ≥ 8 and ≤ 25 .
5. Pre-ictal mRS score of 0 or 1.
6. The interventionalist estimates that at least one deployment of the EmboTrap device can be completed within 8 hours from the onset of symptoms.
7. Patients for whom IV-tPA is indicated and who are available for treatment, are treated with IV-tPA.
8. IV t-PA, if used, was initiated within 3 hrs of stroke onset (onset time is defined as the last time when the patient was witnessed to be at baseline), with investigator verification that the subject has received/is receiving the correct IV t-PA dose for the estimated weight.
9. Angiographic confirmation of an occlusion of an ICA (including T or L occlusions), M1 or M2 MCA, VA, or BA with mTICI flow of 0 – 1.
10. For strokes in the anterior circulation, the following imaging criteria should also be met:
 - a. MRI criterion: volume of diffusion restriction visually assessed ≤ 50 mL.
OR
 - b. CT criterion: ASPECTS 6 to 10 on baseline CT or CTA-source images, or, volume of significantly lowered CBV ≤ 50 mL.
11. The patient is indicated for neurothrombectomy treatment by the Interventionalist and it is confirmed by diagnostic angiography that the device will be able to reach the target lesion proximally.

6.3 Exclusion criteria

Subjects must NOT meet ANY of the exclusion criteria listed below:

1. Life expectancy likely less than 6 months.
2. Females who are pregnant or breastfeeding.
3. History of severe allergy to contrast medium.
4. Known nickel allergy at time of treatment.
5. Known current use of cocaine at time of treatment.
6. Patient has suffered a stroke in the past 3 months.
7. The patient presents with an NIHSS score <8 or >25 or is physician assessed as being in a clinically relevant uninterrupted coma.
8. Subject participating in another study involving an investigational device or drug.
9. Use of warfarin anticoagulation or any Novel Anticoagulant with International Normalized Ratio (INR) >3.0.
10. Platelet count <50,000/ μ L.
11. Glucose <50 mg/dL.
12. Any known hemorrhagic or coagulation deficiency.
13. Unstable renal failure with serum creatinine >3.0 or Glomerular Filtration Rate (GFR) <30.
14. Patients who have received a direct thrombin inhibitor within the last 48 hours; must have a partial thromboplastin time (PTT) less than 1.5 times the normal to be eligible.
15. All patients with severe hypertension on presentation (SBP > 220 mmHg and/or DBP > 120 mm Hg). All patients, in whom intravenous therapy with blood pressure medications is indicated, with hypertension that remains severe and sustained despite intravenous antihypertensive therapy (SBP >185 mmHg and/ or DBP >110 mmHg).
16. Known cerebral vasculitis.
17. Rapidly improving neurological status.
18. Clinical symptoms suggestive of bilateral stroke or stroke in multiple territories.
19. Ongoing seizure due to stroke.
20. Evidence of active systemic infection.
21. Known cancer with metastases.
22. Computed tomography (CT) or Magnetic Resonance Imaging (MRI) evidence of recent/fresh hemorrhage on presentation.
23. Baseline computed tomography (CT) or MRI showing mass effect or intracranial tumor (except small meningioma).
24. Suspicion of aortic dissection, presumed septic embolus, or suspicion of bacterial endocarditis.
25. Stenosis, or any occlusion, in a proximal vessel that requires treatment or prevents access to the site of occlusion.
26. Evidence of dissection in the extra or intracranial cerebral arteries.
27. Occlusions in multiple vascular territories (e.g., bilateral anterior circulation, or anterior/posterior circulation).

6.4 Roll-in phase

Physicians will be trained in the use of the EmboTrap device before any patient procedures. To further assure protocol compliance, participating sites will be required to conduct some “roll-in” patients prior to the enrolling patients into the study. The number of roll-ins to be conducted is region-specific and takes into account an investigation sites previous experience using the EmboTrap device.

Roll-in patients will be analyzed separately from the patients enrolled in the pivotal study, but the information will be recorded and included with the clinical data reported from the study.

6.4.1 US Sites

Participating sites will be required to conduct two roll-in patients with the EmboTrap device prior to commencing patient enrolment into the pivotal phase of the study.

6.4.2 OUS Sites

As the device is CE marked and currently on the market in Europe, sites who did not participate in the earlier ARISE study will be required to conduct one roll-in patient with the EmboTrap device to confirm the sites’ ability to upload information to the eCRF appropriately. Sites which have already enrolled subjects in the ARISE Study and have successfully uploaded information into the eCRF system will automatically move into the pivotal phase of ARISE II without roll-in patients.

All sites both in the US and OUS will be subject to a monitoring visit with 100% source data verification (SDV) as soon as possible after the enrolment of the first patient. Monitoring will focus on correct adherence to the protocol and the complete and appropriate data entry. Continued participation in the study depends on satisfactory study compliance.

6.5 Study Procedures

6.5.1 Study Flow

Subjects presenting with acute ischemic stroke will be evaluated by the physician, in accordance with their institutional practice, to establish an appropriate treatment plan based on the Subject’s medical condition and available diagnostic screening procedures prior to recruitment in the ARISE II Study. A representative overview of the study flow is shown in Figure 3.

[figure not shown]

Figure 3: Study Flow: Patient is in study from time informed consent is obtained

[figure not shown]

Figure 4: Procedure flow diagram for revascularization with EmboTrap device

6.5.1.1 Screening

Subjects will be screened against the study inclusion/exclusion criteria to determine their initial eligibility. A member of the research team (hospital/institution personnel assigned to the ARISE II Study) should review their eligibility. All subjects screened will be documented on the Screening/Enrolment log, including the reason for non-participation for subjects who do not enroll.

6.5.1.1.1 General Medical Evaluation

- A physical examination and medical history.
- Blood pressure and pulse prior to treatment with the EmboTrap device.
- Concomitant medication at baseline

6.5.1.1.2 Laboratory Evaluation

Blood and/or urine specimens for the following laboratory studies:

1. Pregnancy test (for female patients with childbearing potential)
2. Hemoglobin, and platelet count.
3. Coagulation parameters: activated partial thromboplastin time (aPPT) and international normalized ratio.
4. Kidney function: creatinine or GFR
5. Serum glucose.

6.5.1.1.3 Neurologic Evaluation

Screening NIHSS should be recorded as performed. At screening, an historical mRS will be obtained from the subject or the subject's caretaker.

6.5.1.1.4 Computed tomography or magnetic resonance imaging

Computed tomography (CT) or magnetic resonance imaging (MRI) obtained prior to study enrolment will be used for baseline assessment.

6.5.1.1.5 Procedural angiography

Angiography obtained during the procedure will consist of a baseline angiogram, post-device use angiograms (if applicable), a post-final EmboTrap device use angiogram, and if rescue therapy is used, a final post-procedure angiogram.

Baseline angiogram will be obtained prior to device deployment to assess inclusion exclusion criteria as well as to assess clot location. Post-device use angiograms will be obtained immediately after completion of each EmboTrap device and/or rescue therapy pass. The primary endpoint assessment angiogram will be considered any angiogram achieving a rating of mTICI 2b or greater reperfusion, after 3 or less passes of the EmboTrap device, or in the case this is not achieved, the third post EmboTrap device use angiogram. The final post-procedure angiogram will be obtained after all treatments, including any rescue therapies, have been completed. The final post procedure angiogram should comprise a full A-P lateral image.

CT or MRI will also be obtained at 24 hours (16–36 hours) post-procedure to assess any presence

of hemorrhage. It is preferred, but not required, that whether CT or MRI is taken at baseline, to make direct comparison easier, the same imaging modality is obtained at follow-up.

6.5.1.2 *Adverse Events*

Record any adverse events which occur during the procedure.

The procedure description follows.

6.5.2 *Preparation & Delivery*

- Using standard interventional techniques access the arterial system and using angiography, determine the location of the occluded vessel.
- Advance an appropriate Guide Catheter, Sheath or Balloon Guide Catheter as close to the occlusion as possible. Connect a rotating hemostasis valve (RHV) to the proximal end of this catheter and connect to a continuous flush system.
- Select an appropriate Microcatheter. Connect an RHV to the proximal end of the Microcatheter and connect to a continuous flush system.
- With the aid of a suitable guidewire, and using standard catheterization techniques and fluoroscopic guidance, advance the Microcatheter up to and across the occlusion so that the distal end of the Microcatheter is positioned distal of the occlusion.
- Remove the guidewire from the Microcatheter and, if desired, gently infuse contrast media through the Microcatheter to visualize the distal end of the occlusion.
- Remove the Insertion Tool with the preloaded Device from the packaging hoop, taking care not to accidentally retract or advance the Device from the Insertion Tool while doing so.
- Insert the distal end of the Insertion Tool through the RHV of the Microcatheter and wait until fluid is seen exiting the proximal end of the Insertion Tool, confirming that the Device is flushed. Advance the Insertion Tool until it contacts the hub of the Microcatheter. Fully tighten the RHV to hold the Insertion Tool securely in position.
- Confirm that the Insertion Tool is fully seated in the hub of the RHV before proceeding to advance the Device. Advance the Device until at least half of the shaft length has been inserted into the Microcatheter, at which point the Insertion Tool may be removed.

6.5.3 *Positioning and Deployment*

- Continue to advance the Device until the distal radiopaque tip of the Device aligns with the distal tip of the Microcatheter.

Note: There are two silver bands positioned on the proximal portion of the Device shaft to assist in minimizing the amount of fluoroscopic exposure required during Device insertion. If using a standard Microcatheter (total length of 155cm and a 7cm RHV), then when the first silver band on the shaft approaches the RHV, the Device tip will be approximately 8cm from the distal end of the Microcatheter. When the second silver band on the Device shaft approaches the RHV the Device tip will be nearing the distal end of the Microcatheter.

- Advance the Device in the Microcatheter and position the EmboTrap within the clot as described in the Instructions for Use.
- While stabilizing the Device shaft, retract the microcatheter to deploy the Stent-like assembly within the clot. The EmboTrap will be fully deployed once the distal tip of the microcatheter has been retracted to a position over the proximal radiopaque coil of the Device.
- The EmboTrap should be left to embed within the clot for 3-5 minutes prior to withdrawal.

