5.1 Study objectives

The study objective is to examine the recanalization efficacy of the EmboTrap device and its associated performance characteristics and to record associated clinical outcomes in a

manner that facilitates relevant comparison of outputs with that of devices approved in the U.S. for clearing Large Vessel Occlusions.

5.2 **Study endpoints**

5.2.1 **Primary Efficacy endpoint**

The primary efficacy endpoint of the study is revascularization measured using modified Thrombolysis in Cerebrovascular Infarction (mTICI inclusive of the 2c rating). Successful achievement of the endpoint is defined as achieving an mTICI score of 2b or greater in the target vessel, following 3 or less passes of the EmboTrap device. The mTICI result will be based on the final angiogram after the total number of EmboTrap passes performed up to the maximum 3 passes allowed as adjudicated by the Core Lab or the final angiogram after attempted recanalization with the EmboTrap Revascularization Device if rescue devices were used.

Use of rescue therapy, prior to taking the primary endpoint angiogram, is a protocol violation and the resultant angiogram outcomes will be considered failures to achieve the primary endpoint irrespective of mTICI score.

In this single arm study physicians were not precluded from using rescue therapy in the patient post completion of the Primary Efficacy imaging angiogram, this is because more than one vessel, or a previously not visible distal occlusion, may require treatment to achieve a patient optimum outcome. If the physician had a preference for using a smaller device to treat the patient in a distal location or in another vessel this was not precluded.

In a randomised study where both devices would be similarly treated in terms of the use of rescue therapy, and the options for rescue therapy are more limited, a different approach may have been appropriate. As ARISE II was conducted over two continents there were a wide range of device options available to European interventionalists. It would not be appropriate to diminish the efficacy rate reported for EmboTrap by moving all scores of 2b achieved within 3 passes to consider them fails if the interventionalist chose to continue to treat the patient with an alternative device in line with the guidance in the study protocol.

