The modified TICI (mTICI) result for assessing the primary efficacy endpoint for a subject will be taken from the final core laboratory adjudicated angiographic result with EmboTrap (within 3 passes).

5.2.2 **Primary Safety endpoint**

The primary safety endpoint will be measured as the confirmed occurrence of Symptomatic Intracerebral hemorrhage (sICH) within 24 hours (-8/+12 hrs) post-procedure, together with any other Serious Adverse Device Effects (excluding those already counted in sICH).

5.2.3 **Secondary endpoints**

For patients on whom rescue therapy was employed during the procedure, those secondary endpoints related to neurological outcomes observations will be removed from the data set as detailed in the protocol CIP003 rev 05 and these patients excluded from the main analysis of Good clinical outcome (mRS) and Neurological deterioration. This treatment will apply to the following secondary endpoints:

- **Good clinical outcome** – judged to be an mRS score of ≤2 at 90(+/-14) days.
- **Neurological deterioration** – defined by an increase of 4 points or more on the NIHSS score, at the 24-hour time point.

Sensitivity analysis will be performed to assess the robustness of results for these two endpoints to variations in how rescue therapy is defined to define the success of failure to reach an endpoint (Section 10.8).

For the statistical analysis of remaining secondary endpoints, rescue therapy will not be a consideration.

- **Procedure Time** – the time from groin puncture to final angiographic result.
- **Time to treat** - the time from angiographic visualization of large vessel occlusion to achievement of \geq mTICI 2b, or if not achieved, final angiogram. The number of passes to get to mTICI 2b or greater flow will also be recorded.
- **Mortality post-procedure** – All procedure-related mortality (i.e. directly traceable to a procedure- related SAE) at Day 7 post-procedure and all-cause mortality at 90(+/-7) days post-procedure.
- **Serious Adverse Device Effect (SADE)** – CEC confirmed that the EmboTrap device caused, or cannot be ruled out as having caused, an effect that has resulted in any of the consequences characteristic of a serious adverse event.
- **Procedure Related Serious Adverse Events (PRSAE)** – CEC confirmed that the interventional procedure caused, or cannot be ruled out as having caused, an effect that has resulted in any of the consequences characteristic of a serious adverse event.

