Procedure Time will be derived by calculating the time from when the groin was punctured until the acquisition time for the final post treatment confirmation of angiography result (i.e. the time from groin puncture to visualization/acquisition of the final angiographic result).

Time to Treat will be derived by calculating the time between the last time recorded for angiographic confirmation of the large vessel occlusion and the first time TICI 2b or greater was recorded angiographically, or if TICI 2b or greater was not achieved, the time of last angiographic acquisition.

Other sources of endpoint data are:

- All procedure-related mortality at day 7 post-procedure
- All-cause mortality at 90(+/-14) days post-procedure.
- Serious Adverse Device Effects (SADE).
- Procedure Related Serious Adverse Events (PRSAE).
- Symptomatic ICH (sICH).
- Neurological deterioration – defined by an increase of 4 points or more on the NIHSS, at the 24-hour time point.
- Evidence of Infarction of a previously uninvolved vascular territory, as evaluated from 24-hour imaging (CT/MRI).

A summary of all endpoints and the relevant outcome variables are listed in Table 1.

Table 1: Summary of endpoints and relevant outcomes

	Outcomes	Variable type	Notes
Primary Efficacy	mTICI	Binary	
 1. Value 1 = TICI 2b, TICI 2c or TICI 3 (favourable) achieved in the final Embotrap pass within 3 passes. 2. Value 0 = TICI 0, TICI 1 or TICI 2a (adverse) 3. All patients treated with Rescue therapy prior to taking of endpoint assessment angiogram count as fails.=0
Primary Safety	Symptomatic ICH (sICH) + Serious Adverse Device (SADE)	Binary	
 1. Occurrence of either (count only 1 per subject) 2. Within 24 hours (-8/+12 hrs) 3. Values: 1 = favourable, 0 = adverse
Secondary	Good clinical outcome	Binary	
 1. Judged to be an mRS score of ≤ 2 at 90(+/-14) days 2. Values 1 = favourable, 0 = adverse 3. Values for patients in whom rescue therapy was used will be excluded from the primary analysis 4.
	Procedure Time	Continuous (positive)	
 1. Defined as the time from groin puncture to visualization of the final angiographic result 2. Recorded in minutes. 3. No censoring of times 4. Lower value is more favourable

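### The protocol and the SAP name different angiograms for the primary efficacy score, so the primary success rate could depend on which rule is applied

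*Protocol*

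**What the plan says.** **Protocol.** Section 3.1 defines success as mTICI 2b or better in the target vessel within three EmboTrap passes and does not say which angiogram is read. Section 6.5.1.1.5 does: "The primary endpoint assessment angiogram will be considered any angiogram achieving a rating of mTICI 2b or greater reperfusion", within the three-pass limit, "or in the case this is not achieved, the third post EmboTrap device use angiogram". This is a best-of-passes rule, and its fallback angiogram does not exist when fewer than three passes are made.

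**SAP.** Section 5.2.1 gives another rule: "The mTICI result will be based on the final angiogram after the total number of EmboTrap passes performed up to the maximum 3 passes allowed". The section closes by restating it, and Table 1 codes a success only if 2b or better was "achieved in the final Embotrap pass within 3 passes". This is a last-pass rule.

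**The cross-reference.** SAP 5.4 and 13.1 return to the general definition, require that no rescue therapy preceded the assessment angiogram, and add a parenthesis pointing to revision 05 of the protocol. The parenthesis may define rescue therapy or the assessment angiogram. On the second reading it brings protocol 6.5.1.1.5 back into the SAP.

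The SAP revision history lists no change to the scored angiogram, the SAP gives no reason for departing from the protocol on this point, and Table 4 does not compare the two scorings.

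**The concern.** The primary numerator has two definitions that part company for one type of patient: 2b or better on an early pass, below 2b on the last EmboTrap pass.

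Such a patient is possible. The text does not require the operator to stop at 2b (the procedure diagram, protocol Figure 4, was not checked). The operator decides on further passes during the procedure, whereas the score that counts is the core lab's independent reading (protocol 6.5.10). Protocol 4.2 lists clot fragmentation, distal emboli and new thrombus among the risks.

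Because an angiogram is taken after every pass, both rates can be computed from the same data. In an open-label, single-arm trial with one confirmatory test, that leaves a choice of primary rule open at analysis.

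**Working it through.** **1. The rules applied to patient patterns** (core-lab scores, no rescue therapy)

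| Pattern | Protocol 6.5.1.1.5 | SAP 5.2.1 and Table 1 |
|---|---|---|
| 2b after pass 1, stop | success | success |
| 2a, then 2b, stop | success | success |
| 2b, then 2a, stop | success | failure |
| 2a after each of three passes | failure | failure |
| 2a, then 2a, stop | no third angiogram to read | failure |

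Only the third row moves a patient between success and failure. The last row is a gap in the protocol's fallback. It adds no success, since 2b was never reached.

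Let d be the share of patients in the third row. Success on the final pass implies success on some pass, so

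any-angiogram rate = final-angiogram rate + d, with d ≥ 0.

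**2. The plan's own design figure**

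Inputs (protocol 8.2, SAP section 7): n = 176, goal 0.56, assumed rate 0.68, one-sided exact binomial test at 0.025. The pass mark is the smallest r with P(X ≥ r | 176, 0.56) ≤ 0.025.

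- r = 111 (63.1%): p = 0.0342, Wilson lower limit 0.557. Does not meet the goal.
- r = 112 (63.6%): p = 0.0240, Wilson lower limit 0.563. Meets the goal.
- Power at 0.68: P(X ≥ 112 | 176, 0.68) = 0.906.

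The stated 90% power at 176 therefore reproduces.

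**3. How many discordant patients change the conclusion**

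With 112 any-angiogram successes, one discordant patient leaves 111 on the final angiogram and the goal is missed. At the planning rate, 0.68 × 176 = 119.7, or about 120 successes. It would then take 120 − 111 = 9 discordant patients (9/176 = 5.1%) to change the conclusion.

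**4. Illustration over an assumed range of d**

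The documents give no value for d, so 1% to 3% is an assumption. The false-pass column sets the final-angiogram rate at 0.56 and computes P(X ≥ 112 | 176, 0.56 + d). The power column sets the any-angiogram rate at 0.68 and computes P(X ≥ 112 | 176, 0.68 − d).

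| d | Patients (176 × d) | Pass probability, any-angiogram scoring, final rate 0.56 | Power, final-angiogram scoring, any rate 0.68 |
|---|---|---|---|
| 0 | 0 | 2.4% | 90.6% |
| 1% | 1.8 | 4.4% | 84.8% |
| 2% | 3.5 | 7.4% | 77.2% |
| 3% | 5.3 | 12.0% | 67.9% |

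The third column is an error rate only if the final-angiogram rate is the quantity the 0.56 goal refers to.

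**The case against.** The strongest reply is that the SAP governs the analysis, states the stricter last-pass rule three times, and is where protocol 8.3.5 says statistical departures belong. The stricter rule is therefore the one most likely to be applied. That stands as a forecast, but it does not close the point. Protocol 8.3.5 also asks for a rationale, the SAP gives none, and the cross-reference in SAP 5.4 and 13.1 leaves the protocol rule arguable.

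Four stronger readings are tempting and are not supported:

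- **That the two rules do give different rates.** They differ only if at least one patient loses 2b on a later EmboTrap pass, and no frequency is given.
- **That any-angiogram scoring inflates the type I error.** An endpoint defined on any angiogram has its own null at 0.56 and is tested at 2.4%. Inflation follows only if the goal was built on final-angiogram results. The goal comes from TREVO 2 and SWIFT, and neither document says which angiogram those trials scored.
- **That protocol section 6 makes the discordant patient a failure.** The sentence beginning "Vessel recanalization and revascularization based on the final post-EmboTrap device use angiogram" explains why the endpoint was chosen. It fits the SAP rule but does not set a scoring rule.
- **That the choice changes which rescue uses count as failures.** For rescue given after the last EmboTrap pass, the rescue classification is the same under both rules. It could differ only if EmboTrap were used again after rescue, a sequence the documents do not discuss.

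It is also fair to say that the 112 mark applies only if exactly 176 patients are analysed. Up to 228 may be enrolled, and the primary analysis uses ITT patients with a non-missing mTICI score.

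**Conclusion.** The point holds as an unresolved conflict over which angiogram is scored for the primary endpoint. The protocol takes any angiogram at 2b or better within three passes, the SAP takes the final one, and the SAP's cross-reference can be read either way. Its effect runs in one direction: the any-angiogram rate is never the lower of the two.

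The size is unknown. It is zero if no patient loses 2b, decisive with one such patient at the 112/176 boundary, and unlikely to matter if success is near the planned 68% and such patients are few. The 4.4%, 7.4% and 12.0% figures are illustrative: they assume 1%, 2% and 3% discordance and take the final-angiogram rate as the target. The sample size calculation is sound. This should be settled before analysis, but it does not undermine the design.

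**What to change.** Before database lock:

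1. In SAP 5.4 and 13.1, state that the scored angiogram is the final core-lab-adjudicated EmboTrap angiogram within three passes, whatever the number of passes made. Reword the parenthesis so that it clearly refers to the definition of rescue therapy only.
2. Record this in the SAP as a departure from protocol 6.5.1.1.5, with its rationale, as protocol 8.3.5 requires. The alternative is to reconcile the protocol sentence, which needs a formal amendment under protocol section 9. As the SAP already describes enrolment in the past tense, the SAP route is the more practical.
3. Add a row to SAP Table 4 that re-scores primary efficacy on any angiogram at 2b or better within three passes, and report the number of discordant patients.

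The last-pass rule is the natural choice because SAP 5.2.1 and Table 1 already state it and it does not credit flow that was lost again.

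The cost is a few sentences and one more table. No new data are needed, since angiography after every pass is already required. The primary rate may come out slightly lower than under the protocol rule.
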